Genotyping - Confirmation of patient's HoFH status can be made by either genetic or clinical criteria. If HoFH diagnosis cannot be confirmed by the clinical criteria listed or from previous genotyping results, patients may enter the run-in period to determine their mutation status.

Screening Period:

Patients who are required to enter a 2-week screening period:

- Evinacumab treatment-naïve patients.
- Patients from a previous evinacumab study who do not enter this study within 7 days of completing the end of study (EOS) visit of the previous study.

Open-Label Treatment Period:

Patients who completed the EOS visit in the previous evinacumab study within 7 days of the baseline/day 1 visit for this open label study do not have to undergo the screening visit and may enroll directly into this study if they fulfill all of the inclusion criteria and none of the exclusion criteria.

The EOS visit from the previous study can serve as the baseline/day 1 visit for this open-label study and overlapping assessments do not need to be repeated in this study. Baseline assessments and procedures that do not overlap with assessments at the EOS visit of the previous study should be performed after all EOS assessments and procedures have been completed in the previous evinacumab study.

Starting on day 1 (baseline), patients will receive evinacumab 15 mg/kg IV administered Q4W (± 7 days) at the study site. Patients will remain in the clinic for monitoring for 60 minutes after the end of each IV infusion. For patients unable to go to the site, evinacumab may be administered at an alternative location, which could include the patient's home by a trained nurse or other health professional, as allowed by local laws.

All patients who were supplied with alirocumab 150 mg subcutaneous (SC) by the sponsor in a previous study may continue to be provided with alirocumab 150 mg SC every 2 weeks (Q2W) in this study. Those entering this study, after completing a study evaluating the safety and efficacy of alirocumab in patients with HoFH, but did not participate in a prior evinacumab study, may or may not remain on alirocumab as part of their background LMT.

Based on the patient's preference and the judgment of the investigator and the patient's health care provider, each patient may:

- continue treatment with alirocumab supplied by the sponsor as part of their background LMT
- discontinue alirocumab prior to enrolling

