- ² All patients who are on a stable background LMT will enter a 2-week screening period except for those from a previous evinacumab study who completed an end of study visit within 7 days prior to the baseline/day 1 visit for this open-label study.
- ³. Patients who completed an end of study visit in a previous evinacumab study within 7 days of the baseline/day 1 visit for this open-label study do not have to undergo the screening visit and may enroll directly into this study. The EOS visit from the previous study can serve as the baseline/day 1 visit for this open-label study and overlapping assessments do not need to be repeated in this study. Only those assessments and procedures not done in the previous study must be conducted at the baseline visit. These specific assessments to be administered to all patients are identified in the Schedule of Events, [Table 3](#).
- ⁴. Starting on day 1 (baseline), patients will receive evinacumab 15 mg/kg IV administered Q4W.
- ⁵. Patients will be followed for 24 weeks after receiving the last dose of study drug. Patients who enter a CUP, EAP, or ISS/IST may forgo the 24-week follow-up period after the last dose. For these patients, the EOT visit will be their last visit.

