‡ Periodic abstinence (calendar, symptothermal, post-ovulation methods), withdrawal (coitus interruptus), spermicides only, and lactational amenorrhoea method (LAM) are not acceptable methods of contraception. Female condom and male condom should not be used together.

8. Men who are sexually active with WOCBP and are unwilling to use the following forms of medically acceptable birth control during the study drug treatment period and for 24 weeks after the last injection of study drug: vasectomy with medical assessment of surgical success OR consistent use of a condom. Sperm donation is prohibited during the study and for up to 24 weeks after the last injection of study drug.
9. Age <12 years at the screening visit.
10. Tanner stage <2 at the screening visit.

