New onset of diabetes (NOD) for patients without diabetes mellitus at baseline	No	
No medical history of diabetes as specified in Cardiovascular History and Cardiovascular Risk Factors and Medical History CRF pages, AND Hb1Ac < 6.5% at baseline
 
AND one of the following:
 
Lab criteria: At least 2 values of HbA1c \geq6.5% during the TEAE period. NOTE: For patients with only a single measurement available during the TEAE period, a single value \geq6.5% will be considered and qualify the patient as NOD by default. For patients with several HbA1c measurements but only with the last one \geq6.5%, this single value \geq6.5% will be considered and qualify the patient as NOD by default.
 
OR
 
Lab criteria: At least 2 values of fasting glucose \geq126 mg/dL (7.0 mmol/L). NOTE: For patients with only a single measurement available during the TEAE period, a single value \geq126 mg/dL (7.0 mmol/L) will NOT be considered and will NOT qualify the patient as NOD. For patients with several fasting glucose measurements but only with the last one \geq126 mg/dL (7.0 mmol/L), this single value \geq 126 mg/dL (7.0 mmol/L) will NOT be considered and will NOT qualify the patient as NOD.
 
OR
 
HLT Diabetes mellitus (including subtypes)
 
OR
 
- Initiation of any new concomitant medication for hyperglycemia during the treatment period

Diabetic complication for patients with diabetes mellitus at baseline	No	For patients with medical history of diabetes as specified in Cardiovascular History and Cardiovascular Risk Factors and Medical History CRF pages, each of the following criteria will be considered, respectively:

AESI	Using an e-CRF specific tick box on AE page	Using Standard MedDRA Query (SMQ)/company MedDRA Query (CMQ) or lab data
		
 • Diabetes mellitus or diabetic complication TEAEs using HLTG Diabetic complications, HLT Diabetes mellitus (incl subtypes), and PTs Blood glucose increases, Glycosylated haemoglobin increased, Hyperglycaemia, Hyperglycaemic unconsciousness, and Hyperglycaemic seizure • Changes in diabetic medication dosage (specifically increases in dosage) or initiation of additional diabetic medication
Pancreatitis	Yes	No
Cataracts	No	HLT Cataract conditions
Immune complex diseases	No	SMQ (Narrow) Systemic lupus erythematosus SMQ (Narrow) Vasculitis SMQ (Narrow) Guillain-Barre syndrome

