Visit Window (Day)		±7	±7	±7	±7	±7	±7		
Week	0	4	8	12	16	20	24		
Baseline:									
Informed Consent	X								
Treatment:									
Administer IV Open-Label Study Drug ^{3,4}	X	X	X	X	X	X	X	X	X
Concomitant Medications and Procedures (including LMT and apheresis) ³	X	X	X	X	X	X	X	X	X
Efficacy:									
Lipid Panel ^{3,5}	X		X	X	X		X		X
Specialty Lipid Panel ^{3,5}	X		X		X		X		X
Safety:									
Adverse Events	X	X	X	X	X	X	X	X	X
Physical Examination	X								
Measured Height ⁶	X						X		
Body Weight	X	X	X	X	X	X	X	X	X
Vital Signs ⁴	X	X	X	X	X	X	X	X	X
Electrocardiogram ⁷	X						X		
Tanner Stage ⁶							X		
Contraception Use Reminder	X	X	X	X	X	X	X	X	X
Remind male patients to use condoms	X	X	X	X	X	X	X	X	X
Laboratory Testing²:									
Hematology	X		X		X		X		X

Study Procedure	Baseline ¹	Open-Label Treatment Period						Q4-Week Visit Sequence ¹³	
		2	3	4	5	6	7	A	B
Visit	1								
Day	1	29	57	85	113	141	169		
Visit Window (Day)		±7	±7	±7	±7	±7	±7	±7 days	±7 days
Week	0	4	8	12	16	20	24		
Blood Chemistry	X		X		X		X		X
Sex Hormones ^{6,8}							X		
Serum Pregnancy Test ⁷									
Urine Pregnancy Test ⁹	X	X	X	X	X	X	X	X	X
Urinalysis	X		X		X		X		X
hs-CRP	X		X		X		X		X
HbA1C	X			X			X		
Research Samples	X		X				X		X
ADA Samples ¹⁰	X						X		
Pharmacokinetics (PK) of Evinacumab ^{11,12}	X ¹²	X ^{12,17}	X ^{12,17}	X ¹²	X ^{12,17}	X ^{12,17}	X ¹²	X ^{12,17}	
Optional DNA sample ¹⁶									
Other:									
Review of Diet	X	X	X	X	X	X	X	X	X
Reminder of LMT Compliance	X	X	X	X	X	X	X	X	X

Study Procedure	Q4-Week Visit Sequence ¹⁰				End of Treatment (4 weeks post last dose)/ Early Termination Visit ¹⁴	24-Week Follow-up Period				
	C	D	E	F		PV 8 weeks post last dose ¹⁵	12 weeks post last dose	PV 16 weeks post last dose ¹⁵	20 weeks post last dose	24 weeks post last dose/ End of Study Visit
Visit										
Visit Window (Day)	±7	±7	±7	±7		F/U ±5	F/U ±5	F/U ±5	F/U ±5	F/U ±5
Treatment:										
Administer IV Open-Label Study Drug ³	X	X	X	X						
Concomitant Medications and Procedures including LMT and apheresis) ³	X	X	X	X	X	X	X	X	X	X
Efficacy:										
Lipid Panel ^{3,5}	X	X		X	X		X			X
Specialty Lipid Panel ^{3,5}		X		X	X		X			X
Safety:										
Adverse Events	X	X	X	X	X	X	X	X	X	X
Physical Examination										X
Measured Height ⁶				X	X					X
Body Weight	X	X	X	X	X					X
Vital Signs ⁴	X	X	X	X	X		X		X	X
Electrocardiogram ⁷				X	X					X
Tanner Stage ^{6,8}				X	X					X
Contraception Use Reminder	X	X	X	X	X	X	X	X	X	X
Remind male patients to use condoms	X	X	X	X	X	X	X	X	X	X

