Study Procedure	Q4-Week Visit Sequence ¹⁰				End of Treatment (4 weeks post last dose)/ Early Termination Visit ¹⁴	24-Week Follow-up Period				
	C	D	E	F		PV 8 weeks post last dose ¹⁵	12 weeks post last dose	PV 16 weeks post last dose ¹⁵	20 weeks post last dose	24 weeks post last dose/ End of Study Visit
Visit										
Visit Window (Day)	±7	±7	±7	±7		F/U ±5	F/U ±5	F/U ±5	F/U ±5	F/U ±5
Laboratory Testing²:										
Hematology		X		X	X		X		X	X
Blood Chemistry		X		X	X		X		X	X
Serum Pregnancy Test ⁹					X					X
Urine Pregnancy Test ⁹	X	X	X	X		X	X	X	X	X
Urinalysis		X		X	X					X
hs-CRP		X		X	X					X
HbA1C	X			X	X		X			X
Research Samples				X	X					X
ADA Samples ¹⁰				X	X					X
Pharmacokinetics (PK) of Evinacumab ^{11,12}	X ¹²			X ¹²	X					X
Optional DNA Sample ¹⁶	X									
Other:										
Review of Diet	X	X	X	X	X	X	X	X	X	X
Reminder of LMT Compliance	X	X	X	X	X	X	X	X	X	X

10.6.1. Footnotes for Schedule of Events Table 7

1. All evinacumab-naïve patients will enter the screening period. Patients who participated in a previous evinacumab study and who completed an end of study visit in the previous evinacumab study within 7 days prior to the baseline/day 1 visit for this open label study do not have to enter the screening period and may enroll directly in this study. Patients from previous evinacumab studies who do not enter this study within 7 days of completing the EOS visit of the previous study, must undergo screening.
2. For patients undergoing apheresis: Study assessments should be performed and blood samples should be collected immediately before the lipoprotein apheresis procedure.
3. Fasting sample will be collected for the lipid panel: TC, calculated LDL-C, HDL-C, TG, and non-HDL-C, and the specialty lipid panel: Apo B, ratio of Apo B/Apo A-1, Lp(a), and ApoCIII.
4. Electrocardiograms should be performed before blood samples are collected at visits requiring blood draws.
5. Assessment of Tanner Stage, sex hormones, and post-baseline height only applicable to patients < 18 years old.
6. Sex hormones include luteinizing hormone, FSH, estradiol, and total testosterone.

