9. DNA sample for HoFH genotyping should be taken only for patients who have not been enrolled in a previous evinacumab or alirocumab clinical study.

10.6.3. Footnotes for Schedule of Events Table 9

[figure not shown]
1. For patients directly transitioning from a previous evinacumab study: all assessments and procedures should be performed after end of study assessments and procedures have been completed in the previous study, if applicable. Only assessments not performed at the previous end of study visit need to be performed-at the baseline visit.
2. All laboratory samples should be collected before administration of study drug.
3. Study assessments should be performed and blood samples should be collected before study drug administration. For patients undergoing apheresis: Study assessments should be performed and blood samples should be collected before the lipoprotein apheresis procedure; Every effort should be made for the patient to receive study drug immediately after completion of the apheresis procedure, but patients can receive study drug 1 day before the apheresis procedure. The timing between the baseline sample collection relative to the most recently completed LDL apheresis procedure, administration of a PCSK9 inhibitor or mipomersen should match the timing of the week 24 sample collection relative to the most recently completed LDL apheresis procedure, administration of a PCSK9 inhibitor or mipomersen. Depending on the duration between the apheresis procedure and sample collection, the visit window may not apply.
4. Vital signs (temperature, sitting blood pressure, pulse, and respiration rate) should be measured before study drug administration on days when study drug is administered. On dosing days, patients should remain in the clinic for 60 minutes after the end of the IV infusion for monitoring. Pulse and blood pressure should be measured 30 and 60 minutes after the end of the IV infusion.

5. Fasting sample will be collected for the lipid panel: TC, calculated LDL-C, HDL-C, TG, and non-HDL-C, and the specialty lipid panel: Apo B, ratio of Apo B/Apo A-1, Lp(a), and ApoCIII.
6. Assessment of Tanner Stage, sex hormones, and post-baseline height only applicable to patients < 18 years old.
7. Electrocardiograms should be performed before blood samples are collected at visits requiring blood draws.
8. Sex hormones include luteinizing hormone, FSH, estradiol, and total testosterone.

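### Direct rollovers have no scheduled 1719 assessment behind the age and Tanner exclusions, and the new-onset-diabetes rule can count diabetes that arose in the parent study

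*SAP*

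**What the plan says.** **Entry route.** SAP 10.6.1, footnote 1 (and the matching footnote in Protocol 8.1.1) says that previous-study patients with an EOS visit within 7 days before day 1 "do not have to enter the screening period and may enroll directly in this study". Previous-study patients "who do not enter this study within 7 days of completing the EOS visit of the previous study, must undergo screening". Evinacumab-naïve patients are always screened. The point therefore concerns direct rollovers only.

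**Eligibility.** Protocol 5.1 says direct rollovers "may enroll directly into this study if they fulfill all of the inclusion criteria and none of the exclusion criteria"; SAP 4.1 repeats this. Protocol 6.2.3 #10 excludes "Tanner stage <2 at the screening visit", and #9 sets the age limit of 12 years at the same visit.

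**Baseline visit.** Note 3 to Protocol Figure 1 refers the reader to Table 3: "These specific assessments to be administered to all patients are identified in the Schedule of Events". SAP 10.6.3, footnote 1 adds: "Only assessments not performed at the previous end of study visit need to be performed-at the baseline visit".

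**Diabetes.** SAP 10.3, Table 2 limits new-onset diabetes to patients with "No medical history of diabetes as specified in Cardiovascular History and Cardiovascular Risk Factors and Medical History CRF pages" who also have a baseline HbA1c below 6.5%. The diabetic-complication group is defined by a history of diabetes on the same CRF pages. SAP 6.1 sets baseline for 1629 patients at the last value before the first double-blind dose in 1629, and SAP 5.8 applies that to all safety analyses. SAP 4.8.1 starts the TEAE period at the first open-label dose in 1719.

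**The concern.** There are two separate gaps.

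First, an eligibility rule is tied to a visit that one entry route does not contain, and that route's schedule does not collect the information elsewhere before dosing. For a direct-rollover adolescent, nothing scheduled in 1719 documents that exclusion #10 was checked. The SAP also lists Tanner stage as a baseline characteristic for adolescents without saying where it comes from for these patients. Long-term safety in adolescents is a primary objective.

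Second, the at-risk group for new-onset diabetes is fixed at one time and events are counted from another. For 1629 patients the HbA1c condition looks back to before the parent study's treatment, while events count only from 1719 entry. Diabetes that began in between, possibly while on placebo in 1629, can be reported as new onset on open-label evinacumab. New-onset diabetes is an adverse event of special interest, so this enters the main safety reporting.

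**Working it through.** No formula applies to the core of this point, and the plan has no figure to reproduce: both documents state that no sample-size calculation was made. The check is a row-by-row reading of the schedules, followed by tracing one patient through the diabetes rule.

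**Step 1. Schedules side by side**

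| Item | Screening tables (Protocol 1–2, SAP 7–8) | Baseline column (Protocol 3, SAP 9) | First mark in Protocol 3 / SAP 9 |
|---|---|---|---|
| Inclusion/exclusion check | Yes | No row | None |
| Medical/surgical history | Yes | No row | None |
| Tanner stage (<18 years) | Yes | Row, not marked | Week 24 (day 169) |
| Sex hormones (<18 years) | Yes | Row, not marked | Week 24 (day 169) |
| Height | Yes | Marked | Baseline |
| Physical examination | Yes | Marked | Baseline |
| Concomitant medications | Yes | Marked | Baseline |
| HbA1c | No | Marked | Baseline |

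The footnote on direct transitions can only remove items from the Baseline column, when they were done at the parent EOS visit. It cannot add an item that the column lacks. SAP 4.1 rolls overlapping EOS data into the 1719 database but does not name Tanner stage, sex hormones or history.

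**Step 2. Exclusions #9 and #10.** Both refer to the screening visit. Direct rollovers have none. Age can be worked out from any record of birth date, so in practice the gap is #10.

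**Step 3. How old the diabetes baseline is.** Protocol 3.2.3 says previous-study patients would have had at least 24 weeks of evinacumab before entry. The pre-double-blind HbA1c is therefore at least 24 weeks old. SAP 5.7.1 confirms that some 1629 patients had placebo first and then open-label evinacumab. With the 24-week double-blind period (Protocol Section 1), their value is at least 24 + 24 = 48 weeks old. This assumes that the 24-week minimum in 3.2.3 holds for them; the length of the parent open-label period is not stated.

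**Step 4. One patient through the rule.** Take a patient with no diabetes and HbA1c below 6.5% before 1629 dosing, who develops diabetes during 1629 and enters 1719 directly.

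1. History condition: met, if the history on file is the parent-study one. No update is scheduled.
2. HbA1c condition: met, because SAP 6.1 takes the pre-1629-dose value. The day 1 HbA1c is collected but is not this patient's baseline.
3. Event: HbA1c is scheduled at weeks 12 and 24. Two values of at least 6.5% satisfy the laboratory criterion, so the patient counts as new onset in 1719.
4. With no diabetes in the recorded history, the same patient is outside the diabetic-complication group.

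The HbA1c part applies to every 1629 patient. The history part applies only to direct rollovers, because 1629 patients who enter later have a history taken at screening.

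**Step 5. Adolescents.** About 14 are planned. Each direct rollover would be 1/14 = 7.1% of them. For an assumed 0 to 4 such patients the share is 0% to 4/14 = 28.6%.

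**The case against.** The best reply is that the criteria are not waived. Protocol 5.1 and SAP 4.1 still demand that every one is met, the parent EOS visit may serve as day 1, and a parent-study Tanner stage may exist. Exclusion #4 covers new or worsening conditions, and physical examination, height, HbA1c, adverse events and concomitant medications are all marked at Baseline. This stands in part. A reader might infer that the Tanner exclusion cannot be applied to this group. The documents do not support that, because a missing schedule entry does not remove the rule. They also do not say that a parent-study value exists or may be used, and none of the safeguards yields a Tanner stage.

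A reader might also infer that pubertal change since entry is lost as an analysis. The SAP plans no Tanner change analysis and its laboratory list omits sex hormones. Under the protocol's general laboratory rule, the baseline for 1629 patients would be the pre-parent-dose value anyway.

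On diabetes, it is fair to say that the source of the 1719 history is unspecified, so calling it outdated is an inference. A glucose-lowering drug begun in 1629 and continuing is recorded as pre-existing and does not count as newly started. The HbA1c condition is a second gate, but for 1629 patients it looks back to the same early time, so it does not close the gap.

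Finally, moving diabetes status to 1719 entry would class diabetes that arose on evinacumab in 1629 as pre-existing. That is a real cost, and it is why such cases need their own listing.

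**Conclusion.** The point holds for two things.

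- **Eligibility:** exclusions #9 and #10 refer to a visit that direct rollovers do not have, and no scheduled 1719 assessment supports them. Protocol 6.2.3 and the schedule must be reconciled.
- **New-onset diabetes:** for 1629 patients the at-risk condition and the event window start at different times, at least 24 weeks apart and at least 48 for placebo-first patients under the assumption above. Diabetes that arose in 1629 can be counted as new onset in 1719. The history part depends on whether sites update it at entry, which the documents do not say.

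The size is small. Protocol Section 1 reports no new-onset-diabetes concern in the 1629 double-blind period, so few cases are expected. The number of direct rollovers is not stated, although the same section names 1629 as the parent study from which most patients continued. The number of direct-rollover adolescents is not given and may be zero, since the added places were meant for evinacumab-naïve adolescents, who are all screened. A reader might extend the point to coronary heart disease status, but that feeds only descriptive history summaries and no efficacy subgroup. The changes are worth making because they are cheap and bear on the adolescent and special-interest safety reporting.

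**What to change.** **Protocol.** Reconcile 6.2.3 #9 and #10 with the schedule by tying them to screening or, if there is none, baseline/day 1. In the Baseline column of Table 3, for direct rollovers, add the eligibility check and an interval medical history. For those under 18, also add Tanner stage and sex hormones unless done at the parent EOS visit. No separate medication history is needed, because concomitant medications are already collected at Baseline. Carry the same entries into SAP Table 9.

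**SAP.** Define at-risk status for new-onset diabetes, and membership of the diabetic-complication group, by diabetes status at 1719 entry, using the updated history and the day 1 HbA1c already collected. Leave the SAP 6.1 baseline for change in HbA1c as it is. List separately diabetes that arose during the parent study, so that it is not lost from the record.

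If direct-rollover enrolment is already complete, the SAP can still name the parent-study record that supplies Tanner stage and history, and state which history and HbA1c define diabetes status.

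**Cost.** A short history update for each direct rollover and, for the few who are adolescents, one Tanner assessment and one hormone assay at a visit that already includes a physical examination and a blood draw.
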